#### **8.4.2 Follow-up of Adverse Event and Serious Adverse Event**

Any AEs that are unresolved at the participant's last visit in the study are followed up by the investigator for as long as medically indicated, but without further recording in the eCRF. AstraZeneca retains the right to request additional information for any participant with ongoing AE(s)/SAE(s) at the end of the study, if judged necessary.

##### **Adverse event variables**

The following variables will be collected for each AE:

- AE (verbatim)
- The date and time when the AE started and stopped
- Maximum intensity of the AE:
  - Intensity rating scale:
    - 1 Mild (awareness of sign or symptom, but easily tolerated)
    - 2 Moderate (discomfort sufficient to cause interference with normal activities)
    - 3 Severe (incapacitating, with inability to perform normal activities)
- Whether the AE is serious or not
- Investigator causality rating against the Investigational Product(s) (yes or no)
- Action taken with regard to Investigational Product(s)
- AE caused participant's withdrawal from study (yes or no)
- Outcome.

In addition, the following variables will be collected for SAEs:

- Date AE met criteria for SAE
- Date investigator became aware of SAE
- AE is serious due to (reason)
- Date of hospitalisation
- Date of discharge
- Probable cause of death
- Date of death
- Autopsy performed
- Causality assessment in relation to Study procedure(s)

- Causality assessment to other medication

### **8.4.3 Causality Collection**

The investigator should assess causal relationship between Investigational Product and each AE, and answer ‘yes’ or ‘no’ to the question ‘Do you consider that there is a reasonable possibility that the event may have been caused by the investigational product?’

For SAEs, causal relationship should also be assessed for other medication and study procedures. Note that for SAEs that could be associated with any study procedure the causal relationship is implied as ‘yes’.

A guide to the interpretation of the causality question is found in [Appendix B](#) to the CSP.

### **8.4.4 Adverse Events Based on Signs and Symptoms**

All AEs spontaneously reported by the participant or reported in response to the open question from the study site staff: ‘Have you had any health problems since the previous visit/you were last asked?’, or revealed by observation will be collected and recorded in the eCRF. When collecting AEs, the recording of diagnoses is preferred (when possible) to recording a list of signs and symptoms. However, if a diagnosis is known and there are other signs or symptoms that are not generally part of the diagnosis, the diagnosis and each sign or symptom will be recorded separately.

### **8.4.5 Adverse Events Based on Examinations and Tests**

The results from the CSP mandated laboratory tests and vital signs will be summarised in the CSR.

Deterioration as compared to baseline in protocol-mandated laboratory values, vital signs ECGs, and other safety assessments should therefore only be reported as AEs if they fulfil any of the SAE criteria, are the reason for discontinuation of treatment with the investigational product or are considered to be clinically relevant as judged by the investigator (which may include but not limited to consideration as to whether treatment or non-planned visits were required or other action was taken with the study treatment, eg, dose adjustment or drug interruption).

If deterioration in a laboratory value/vital sign is associated with clinical signs and symptoms, the sign or symptom will be reported as an AE and the associated laboratory result/vital sign will be considered as additional information. Wherever possible the reporting investigator uses the clinical, rather than the laboratory term (eg, anaemia versus low haemoglobin value). In the absence of clinical signs or symptoms, clinically relevant deteriorations in non-mandated parameters should be reported as AE(s).

Any new or aggravated clinically relevant abnormal medical finding at a physical examination as compared with the baseline assessment will be reported as an AE unless unequivocally related to the disease under study.

#### **8.4.6 Hy's Law**

Cases where a participant shows elevations in liver biochemistry may require further evaluation and occurrences of AST or ALT  $\geq 3xULN$  together with TBL  $\geq 2xULN$  may need to be reported as SAEs. Please refer to [Appendix E](#) for further instruction on cases of increases in liver biochemistry and evaluation of Hy's Law.

#### **8.4.7 Reporting of Serious Adverse Events**

All SAEs have to be reported, whether or not considered causally related to the investigational product, or to the study procedure(s). All SAEs will be recorded in the eCRF.

If any SAE occurs in the course of the study, then investigators or other site personnel inform the appropriate AstraZeneca representatives within one day ie, immediately but **no later than 24 hours** of when he or she becomes aware of it.

The designated AstraZeneca representative works with the investigator to ensure that all the necessary information is provided to the AstraZeneca Patient Safety data entry site **within 1 calendar day** of initial receipt for fatal and life-threatening events **and within 5 calendar days** of initial receipt for all other SAEs.

For fatal or life-threatening adverse events where important or relevant information is missing, active follow-up is undertaken immediately. Investigators or other site personnel inform AstraZeneca representatives of any follow-up information on a previously reported SAE within one calendar day, ie, immediately but **no later than 24 hours** of when he or she becomes aware of it.

Once the investigators or other site personnel indicate an AE is serious in the EDC system, an automated email alert is sent to the designated AstraZeneca representative (or delegate).

If the EDC system is not available, then the investigator or other study site staff reports a SAE to the appropriate AstraZeneca representative by telephone.

The AstraZeneca representative will advise the investigator/study site staff how to proceed.

The reference document for definition of expectedness/listedness is the IB for the AstraZeneca drug.

#### **8.4.8 Pregnancy**

All pregnancies and outcomes of pregnancy should be reported to AstraZeneca except for:

- If the pregnancy is discovered before the study participant has received any study drug

#### **8.4.8.1 Maternal Exposure**

Women of childbearing potential are not allowed to be included in this study. Should a pregnancy still occur, the investigational product should be discontinued immediately and the pregnancy reported to AstraZeneca.

#### **8.4.8.2 Paternal Exposure**

Male participants should refrain from fathering a child or donating sperm during the study and 3 months following the last dose.

Pregnancy of the participant's partners is not considered to be an AE. However, the outcome of all pregnancies (spontaneous miscarriage, elective termination, ectopic pregnancy, normal birth or congenital abnormality), occurring from the date of the first dose until 3 months after the last dose and as indicated by previous studies (preclinical and clinical) should, if possible, be followed up and documented in the Pregnancy Report Form. Consent from the partner must be obtained before the Pregnancy Report Form is completed.

#### **8.4.9 Medication Error**

If a medication error occurs in the course of the study, then the investigator or other site personnel informs the appropriate AstraZeneca representatives within 1 day, ie, immediately but no later than 24 hours of when he or she becomes aware of it.

The designated AstraZeneca representative works with the investigator to ensure that all relevant information is completed within 1 (Initial Fatal/Life-Threatening or follow-up Fatal/Life-Threatening) or 5 (other serious initial and follow-up) calendar days if there is an SAE associated with the medication error (see Section 8.4.7) and within 30 days for all other medication errors.

The definition of a Medication Error can be found in [Appendix B](#).

### **8.5 Overdose**

For this study, any dose of IMP greater than the dose intended to be given will be considered an overdose.

- An overdose with associated AEs is recorded as the AE diagnosis/symptoms on the relevant AE modules in the eCRF and on the Overdose eCRF module.
- An overdose without associated symptoms is only reported on the Overdose eCRF module

If an overdose on an AstraZeneca study drug occurs in the course of the study, the investigator

or other site personnel inform appropriate AstraZeneca representatives immediately, but **no later than 24 hours** of when he or she becomes aware of it.

The designated AstraZeneca representative works with the investigator to ensure that all relevant information is provided to the AstraZeneca Patient Safety data entry site within 1 or 5 calendar days for overdoses associated with an SAE (see section 8.4.7) and within 30 days for all other overdoses.

## **8.6 Human Biological Samples**

Instructions for the collection and handling of biological samples will be provided in the study specific laboratory manual. Samples should be stored in a secure storage space with adequate measures to protect confidentiality. For further details on Handling of Human Biological Sample see [Appendix C](#).

### **8.6.1 Pharmacokinetics**

Venous blood samples will be collected for measurement of plasma concentrations of AZD9567 and prednisolone as specified in the SoA in Section 1.3.

Plasma samples for evaluation of the PK of prednisolone will be collected in this study; these will be reported outside the CSR.

Samples may be collected at additional time points during the study if warranted and agreed upon between the investigator and the sponsor, eg, for safety reasons. The timing of sampling may be altered during the course of the study based on newly available data (eg, to obtain data closer to the time of peak or trough matrix concentrations) to ensure appropriate monitoring.

Samples will be collected, labelled, stored, and shipped as detailed in the Laboratory Manual.

Pharmacokinetic samples will be disposed of after the Bioanalytical Report finalisation or 6 months after issuance of the draft Bioanalytical Report (whichever is earlier), unless consented for future analyses. Pharmacokinetic samples may be disposed of or anonymised by pooling. Additional analyses may be conducted on the anonymised, pooled pharmacokinetic samples to further evaluate and validate the analytical method. Any results from such analyses may be reported separately from the CSR.

#### **8.6.1.1 Determination of Drug Concentration**

Blood samples for determination of drug concentration of AZD9567 and prednisolone will be assayed using an appropriately validated bioanalytical method. Full details of the analytical method used will be described in a separate bioanalytical report.

Drug concentration information that would unblind the study will not be reported to investigative sites or blinded personnel until the study has been unblinded (ie, at database

lock).

Incurred sample reproducibility analysis or additional assay development work, if any, will be performed alongside the bioanalysis of the test samples. The results from the evaluation, if performed, will be reported in a separate Bioanalytical Report.

## **8.6.2 Immunogenicity Assessments (Not Applicable)**

Immunogenicity will not be evaluated in this study.

## **8.6.3 Pharmacodynamics**

### **8.6.3.1 Collection of Samples**

Blood samples will be collected for measurement of TNF $\alpha$  (Section 8.2.4). Urine samples will be collected for measurement of 24-hour U-Na and U-K (Section 8.2.3).

Samples will be collected, labelled, stored, and shipped as detailed in the Laboratory Manual.

For storage, re-use, and destruction of PD samples see [Appendix C](#).

## **8.7 Human Biological Sample Biomarkers**

### **8.7.1 Collection of Mandatory Samples for Biomarker Analysis**

By consenting to participate in the study the participant consents to participate in the mandatory research components of the study. Samples for biomarker research are required and will be collected from all participants in this study as specified in the SoA (Section 1.3).

Samples will be stored for a maximum of 15 years from the date of the issue of the CSR in line with consent and local requirements, after which they will be destroyed/repatriated.

For storage, re-use and destruction of biomarker samples see [Appendix C](#).

## **8.8 Optional Genomics Initiative Sample**

Collection of optional samples for genomics initiative research is also part of this study as specified in the SoA and is subject to agreement in the ICF addendum.

Blood sample for DNA isolation will be collected from participants who have consented to participate in the genetic analysis component of the study. Participation is optional. Participants who do not wish to participate in the genetic research may still participate in the study.

See [Appendix D](#) for information regarding the Genomics Initiative genetic sample. Details on processes for collection and shipment and destruction of these samples can be found either in the appendices or in the Laboratory Manual.

For storage and destruction of genetic samples see [Appendix D](#).

## 8.9 Health Economics/Medical Resource Utilisation and Health Economics (Not Applicable)

Health Economics/Medical Resource Utilisation and Health Economics parameters are not evaluated in this study.

## 9 STATISTICAL CONSIDERATIONS

### 9.1 Statistical Hypotheses

This study aims to demonstrate that AZD9567 improves glucose homeostasis compared to oral prednisolone.

The null hypothesis for the primary analysis is that there is no difference in the change in glucose AUC(0-4) versus baseline in AZD9567 compared to prednisolone following a standardised MMTT. The following comparison will be performed:

- 72 mg AZD9567 versus 40 mg prednisolone in participants with T2DM (Cohort 1)
- 40 mg AZD9567 versus 20 mg prednisolone in participants with T2DM (Cohort 2)
- Placebo versus 5 mg prednisolone in participants with T2DM (Cohort 3)

As this is a Phase 2a study, no adjustments for multiple testing will be performed. Cohorts 2 and 3 are not powered, thus all significance testing should be considered exploratory.

CCI

[REDACTED]

CCI [REDACTED]

[REDACTED]

### 9.3 Populations for Analyses

The following populations are defined in [Table 8](#).

**Table 8 Populations for Analysis**

Population/Analysis set	Description
All Enrolled Participants (ENR)	All participants who sign the ICF prior to any study-related procedures.
All Randomised Participants (RND)	All participants in the ENR randomised to one of the two sequence groups within a cohort. The ENR will be analysed according to the planned sequence or treatment.
Full Analysis Set (FAS)	All participants in the RND who received at least one dose of study intervention. The FAS will be analysed according to the planned treatment and will be used as the primary population for reporting pharmacodynamic data and to summarize baseline characteristics. Any important deviations from randomised treatment will be listed and considered when interpreting the pharmacodynamic data.
Safety Analysis Set (SAF)	All participants in the RND who received at least one dose of study intervention. The SAF will be analysed according to actual treatment.
Per Protocol Analysis Set (PP)	All participants in the FAS who did not have an important protocol deviation considered to have an impact on the analysis of the primary endpoint and who completed the study. The PP will be analysed according to the actual treatment received.
PK Analysis Set (PKAS)	All participants in the FAS with at least one quantifiable AZD9567 concentration and no important protocol deviations, or AEs considered to have an effect upon PK. Participants may be excluded from the PK population if they have an AE of vomiting before 2x the median tmax of the group. Participants in the PKAS will be analysed according to the actual treatment.  This population will be defined by the Study Team Physician, Pharmacokineticist and Statistician prior to any analysis.

### 9.4 Statistical Analyses

The SAP will include a more technical and detailed description of the statistical analyses

described in this section. This section is a summary of the planned statistical analyses of the most important endpoints including primary and key secondary endpoints.

#### **9.4.1 General Considerations**

Analyses will be performed by Parexel, except for the derivation of PK parameters, which will be performed by Covance Clinical Pharmacokinetic Alliance.

Continuous data will be summarised using descriptive statistics (number of observations, mean, SD, median, 25th and 75th percentiles [where appropriate], minimum and maximum). For log-transformed data it is more appropriate to present geometric mean, geometric coefficient of variation, median, minimum and maximum. Frequencies and percentages will be used for summarising categorical (discrete) data. Time parameters (tmax, tlast, etc) will be presented as minimum, median, and maximum only.

Confidence intervals and p-values, when presented, will generally be constructed at the 2-sided 95% level.

Unless otherwise stated, summaries will be presented by cohort and treatment. The treatment comparisons of interest are the different doses of AZD9567 versus the different doses of prednisolone and placebo versus 5 mg prednisolone. No formal comparisons between the different AZD9567 doses will be conducted. Similarly, no formal comparisons between the different prednisolone doses will be conducted.

In general, baseline will be defined as the last observation prior to study intervention in each period. The baseline for CGM/FGM will be the mean of all daily results prior to study intervention. Further details will be described in the SAP.

All statistical analyses will be conducted using SAS® version 9.4.

A complete set of raw data listings will be appended to the final CSR. All tables, figures and listings will be presented as PDF documents without any manual editing (ie, they will appear unmodified as programmed by means of the statistical package).

In general, there will be no imputation of missing data for the safety analyses. Additional details on missing data handling conventions will be provided in the SAP.

Deviations from the protocol will be assessed as “important” or “not-important”. Important deviations from the protocol may lead to the exclusion of participants from any of the study analysis sets. Deviations will be defined before database hard lock. Important deviations will include the following:

- Violation of inclusion and/or exclusion criteria

- Administration of prohibited concomitant medications that are expected to influence the measurement of the primary endpoint.
- Receiving incorrect study intervention than randomised to.

All protocol deviations will be discussed at a data review meeting prior to database hard lock in order to define the analysis sets for the study. All important protocol deviations will be listed by participant. Further details will be provided in the SAP.

## **9.4.2 Pharmacodynamic Effects**

### **9.4.2.1 Primary Endpoint(s)**

The primary pharmacodynamic variable is the change from baseline in glucose AUC(0-4) following a standardised MMTT.

The change from baseline in glucose AUC(0-4) will be analysed using a linear mixed model with baseline included as covariate. Treatment, period, and sequence will be included as fixed effects, with participant within sequence as random effect. Models will be run separately for each cohort.

The following comparisons will be performed:

- 72 mg AZD9567 versus 40 mg prednisolone (Cohort 1).
- 40 mg AZD9567 versus 20 mg prednisolone (Cohort 2).
- Placebo versus 5 mg prednisolone (Cohort 3).

Should there be more than 10% of participants erroneously treated, a sensitivity analysis will be performed on the PP set.

Descriptive statistics and graphical presentations will be presented.

### **9.4.2.2 Secondary Endpoint(s)**

Mean daily glucose as measured by CGM will be evaluated as a secondary endpoint.

The mean daily glucose will be analysed using an MMRM analysis with baseline as covariate. Treatment, period, and sequence will be included as fixed effects, participant within sequence as random effect, and day as repeated measure. Models will be run separately for each cohort.

Similar analyses will be performed for the rise in mean daily glucose over 24-hour periods.

The secondary endpoints (insulin, glucagon, GLP-1, GIP), changes in FFAs during MMTT, C-peptide, 24-hour U-Na and U-K excretion and the ratio between them,  $\Delta I_{10}/\Delta G_{10}$ ,  $\Delta I_{30}/\Delta G_{30}$ ,  $\Delta C_{10}/\Delta G_{10}$ ,  $\Delta C_{30}/\Delta G_{30}$  and C-peptide will be summarised and analysed by means of a linear model or a mixed model for repeated measurements.

LPS-stimulated whole blood TNF $\alpha$  levels will be evaluated as a secondary endpoint for participants in Cohort 1 and Cohort 2 (high and low dose comparison). For TNF $\alpha$  profiles, the AUC will be estimated and the measurements at the sampling points will be summarised. Descriptive statistics will be tabulated both for the AUC and individual measurement points and treatments comparison will be conducted with ANOVA. Models will be run separately for each cohort.

Further details on statistical analyses will be provided in the SAP.

Descriptive statistics and graphical presentations will be presented as appropriate.

#### **9.4.2.3 Tertiary/Exploratory Endpoint(s)**

CCI

#### **9.4.3 Safety**

Safety will be assessed by descriptive analysis of AEs/SAEs, vital signs, ECGs and clinical laboratory assessments.

Serum cortisol and ACTH will be analysed in a similar manner to the TNF $\alpha$  secondary endpoint. Further details on statistical analyses will be provided in the SAP.

##### **9.4.3.1 Adverse Events**

The MedDRA will be used to code AEs.

The number of participants experiencing each AE will be summarised by the MedDRA system organ class and preferred term. The number and percentage of participants with AEs in each different category (eg, causally related, severe, etc) will be summarised, and events in each category will be further summarised by MedDRA system organ class and preferred term.

SAEs will be summarised separately if a sufficient number occur.

Any AE occurring before first study intervention will be included in the data listings but will not be included in the summary tables of AEs. AE summary tables will include only AEs occurring after start of study intervention (first dose).

Any AE occurring after last dosing and up to 21 days after discontinuation of study intervention, within each period, will be included in AE summaries. AEs occurring after 21 days will be listed separately, but not included in summaries.

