## **Appendix B Adverse Events: Definitions and Procedures for Recording, Evaluating, Follow-up, and Reporting**

### **B 1 Definition of adverse events**

An adverse event is the development of any untoward medical occurrence in a participant or clinical study participant administered a medicinal product and which does not necessarily have a causal relationship with this treatment. An AE can therefore be any unfavourable and unintended sign (eg, an abnormal laboratory finding), symptom (for example nausea, chest pain), or disease temporally associated with the use of a medicinal product, whether or not considered related to the medicinal product.

The term AE is used to include both serious and non-serious AEs and can include a deterioration of a pre-existing medical occurrence. An AE may occur at any time, including run-in or washout periods, even if no Study treatment has been administered.

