4.10 Prior and Concomitant Medications, and other treatments

All listings and tables will be based on the Safety Analysis Set.

Medications will be coded using the World Health Organisation-Drug Dictionary (WHODRUG) and will be classified by Anatomical Therapeutic Chemical (ATC) categories.

Exclusively prior medications are those that started and stopped prior to the first dose of the investigational medicinal product (IMP) in the first treatment period and those that started and stopped after 21 days after the last dose in the first period and before the first dose of IMP in the second period. Medications taken between the first dose and up to 21 days after the last dose in any period are concomitant (including medications that started prior to dosing and continued after).

Concomitant medication will be listed by participant and will include the reported name, anatomical therapeutic chemical (ATC), route of administration, total dose, frequency, start date/time, duration, whether or not ongoing and indication and will be summarised by ATC and PT.

CCI**CONFIDENTIAL****Project Document Version No.** Final 2.0**Project Document Effective Date:** <Date of last signature>

Page 29 of 56

Medications ongoing during both the periods will be counted under both Period 1 and Period 2.

Prior and concomitant use of Metformin will be listed by participant and will include the total dose, frequency, start date/time, duration and whether or not ongoing and will be summarised by ATC and PT.

The number of subjects taking concomitant medications under each treatment will be summarised by ATC classification/ Generic term.

The duration will be calculated as:

Duration (in days) = (end date – start date) + 1, if only date is known.

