4.11.1 Adverse Events

Within each cohort, AEs will be assigned as having taken place after each of the two treatments if the start of the AE is after the first dose of the treatment but before the end of 21 days after the last dose (i.e., the end of Day 24, in the case of subjects whose last dose was on Day 3). AEs on Day 1 with a missing start time will be assumed to have started after the first dose.

In order to assign the corresponding SOC and preferred term to each AE, AEs will be coded using the Medical Dictionary for Regulatory Activities (MedDRA) Version 22.1 or higher.

AEs occurring prior to the time of dosing on Day 1 and after 21 days after the last dose will not be included in summaries.

An AE listing for the Safety analysis set will cover details for each individual AE. A summary table with the number of AEs, by SOC and PT will be created.

The following summaries for the number and percentage of participants will be created:

- Number of subjects with adverse events in any of these categories:
 - Any AE
 - Any AE with outcome = death
 - Any SAE (including events with outcome = death)
 - Any AE leading to discontinuation of IP
 - Any AE leading to drug interruption
 - Any AE leading to withdrawal from study
- Number of subjects with adverse events, by SOC and PT
- Number of subjects with adverse events, by PT
- Number of subjects with adverse events leading to discontinuation of investigational product, by system organ class and preferred term.

In summaries including SOC or PT, the summaries will first be sorted by decreasing percentage of participants in each SOC and PT within SOC, and then alphabetically by SOC, and PT within SOC.

The following summaries for the number and percentage of adverse will be created:

- Number of adverse events by system organ class and preferred term.

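### AE tables place events by their start, so an ongoing AE that becomes serious or stops treatment after dosing is left out of the by-treatment counts or credited to the other drug

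*Protocol*

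**What the plan says.** Protocol 9.4.3.1 keeps pre-dose events out of the tables: "Any AE occurring before first study intervention will be included in the data listings but will not be included in the summary tables". It speaks of AEs occurring and does not separate onset from worsening. After the last dose in each period, events are tabulated for 21 days and listed thereafter.

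The operative rule is in SAP 4.11.1. An AE belongs to a treatment "if the start of the AE is after the first dose of the treatment" and before the end of 21 days after its last dose. The same section adds: "AEs occurring prior to the time of dosing on Day 1 and after 21 days after the last dose will not be included" in summaries.

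Other relevant text:

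- Protocol 8.4.1 collects AEs from consent, so a record can be open before dosing.
- The variable list in Protocol 8.4.2 has start and stop times, "Maximum intensity of the AE", the action taken with the product and, for SAEs, "Date AE met criteria for SAE". It has no date of worsening, and no table rule uses the date of seriousness.
- Appendix B 1 says that the term AE "can include a deterioration of a pre-existing medical occurrence". It does not say how to record the worsening of an AE already entered.
- SAP 4.11.1 and 4.11.2 tabulate SAEs, and 4.11.1 tabulates AEs leading to discontinuation. Protocol 9.4.3.1 also promises a summary of severe AEs, but the SAP lists no severity table.

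**The concern.** The safety objective compares AZD9567 with prednisolone, and each participant in Cohorts 1 and 2 takes both. The by-treatment tables carry that comparison. A rule based on onset works for new events. It does not work for an event that is already open when dosing starts and becomes serious, or stops treatment, on drug. Depending on when it began, that event is either absent from the tables or counted against the drug taken in the other period.

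The situation is foreseeable. AEs are recorded through screening, some participants stop an SGLT2 or DPP4 inhibitor two weeks before dosing, and Protocol Table 1 names raised glucose as an early effect of glucocorticoids. The resulting error can favour either treatment.

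**Working it through.** **Inputs.** In the schedule of activities (Protocol 1.3), Period 1 doses fall on study Days 1 to 3 and Period 2 doses on study Days 28 to 30. The window is 21 days after the last dose (SAP 4.11.1). The washout may be extended from 3 to 4 weeks (Protocol 1.3, footnote b). Planned completers are 24 in Cohort 1 and 8 in each of Cohorts 2 and 3.

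**Reproducing the SAP's figure.** Last dose Day 3 + 21 = Day 24. This matches the end of the window given in SAP 4.11.1. For Period 2 the window ends on study Day 30 + 21 = Day 51.

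**Applying the start rule to the nominal schedule (complete dates).**

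| AE starts on study day | Tabulated under |
|---|---|
| Before the Day 1 dose | Neither treatment |
| Day 1 after dosing, to Day 24 | Period 1 treatment |
| Days 25 to 27, or Day 28 before dosing | Neither treatment |
| Day 28 after dosing, to Day 51 | Period 2 treatment |
| After Day 51 | Neither treatment |

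The gap before Period 2 is three full days (25, 26, 27). If the washout is one week longer, the first Period 2 dose moves to Day 35 and the gap becomes 35 − 1 − 24 = 10 days. Study Days 26 and 27 carry safety laboratory samples and a mixed meal test, so findings can arise there.

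**Three cases under this rule.**

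1. The AE starts before Day 1 and becomes serious, or leads to discontinuation, after dosing. It is in no by-treatment table.
2. The AE starts on Days 25 to 27 and does the same in Period 2. It is in no by-treatment table.
3. The AE starts in Period 1, is still open on Day 28 and becomes serious in Period 2. It is tabulated as an SAE of the Period 1 drug.

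**Size of one event**, for a participant with no other event in that row:

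- Cases 1 and 2, any row: 1/24 = 4.2 percentage points in Cohort 1; 1/8 = 12.5 points in Cohorts 2 and 3.
- Case 3, any-AE row: the event did begin under the first drug, so that credit is right. Counting it under the second drug as well changes the difference by 1/24 or 1/8.
- Case 3, SAE row: the event leaves one column and enters the other, so the difference changes by 2/24 = 8.3 points or 2/8 = 25 points. A severe-AE row would behave in the same way.

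**The case against.** The strongest reply is that a worsening may be recorded as a new AE. Appendix B 1 treats deterioration as something an AE can be. Protocol 8.4.5 makes a decline in mandated laboratory values reportable when it is serious, causes discontinuation or is clinically relevant. A first reportable decline after dosing would then have its own on-drug start and be counted properly. This stands in part. A reader might infer that each AE has exactly one record, so that every worsening is lost. The documents do not say so. They list the variables but do not settle whether a worsened AE is updated or re-entered. The intensity part of the problem arises only if sites update the existing record. For the same reason, it should not be inferred that on-drug hyperglycaemia is generally missed. The primary and CGM endpoints also measure glucose directly, against a baseline in each period.

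Other limits also stand:

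- The start rule is in the SAP; the Protocol sentence alone does not show it. It is exact only for complete dates: SAP 4.3.2.1 also uses the end date when the start is incomplete, and SAP 4.11.1 treats a Day 1 event without a time as post-dose.
- Since the SAP has no severity table, intensity affects only the severity summary that the Protocol promises.
- Case 3 is narrow. Dosing lasts three days, a three-week washout follows, and eligibility is checked again before Period 2.
- A reader might apply the 8.3 and 25 point shifts to all tables. They hold only for SAE or severe rows in case 3.
- The SAP says of drugs: "Medications ongoing during both the periods will be counted under both Period 1 and Period 2". This might look like an inconsistency with the AE rule. It is not one, because taking a drug in both periods is a fact of exposure, whereas counting every ongoing AE twice would charge carried-over events to the second drug.

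Finally, the events stay in the listings, all SAEs are recorded, and safety analysis is descriptive in small cohorts. This limits the harm but does not correct the tables.

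**Conclusion.** The point holds for seriousness and discontinuation. SAP 4.11.1 states a rule that yields a wrong by-treatment count for AEs that are open before dosing and become serious or stop treatment on drug, and neither document has a provision that overrides it. For intensity it holds only on the condition about recording given above.

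The documents give no AE rates, so the number of affected events is unknown and may be zero. The per-event sizes assume planned completers as denominators. The safety set includes everyone dosed, so the true percentages would differ slightly. In Cohorts 2 and 3 a single event is a visible share of a row. This is a cheap improvement of low-to-moderate severity; it does not undermine the safety evaluation as a whole.

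**What to change.** In SAP 4.11.1 and 4.3.2.1 and Protocol 9.4.3.1, count an AE for a period's treatment if, from that period's first dose to 21 days after its last dose, it does any of the following:

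- starts;
- becomes serious, using the date already collected for this;
- leads to discontinuation of the investigational product, placed by the recorded dosing dates (Protocol 6.4);
- increases in intensity.

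In the SAE, discontinuation and severity rows, credit the event to the treatment of the period in which that change occurred. State also where an event goes if the change falls between the two windows; leaving it with its treatment of onset keeps it in the tables.

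For intensity, instruct sites to enter a post-dose worsening as a new AE with its own start date and time. This works only prospectively.

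Reconcile rule 1 of SAP 4.3.2.1 with 4.11.1. Read literally, it makes events on-treatment from the point at which 4.11.1 closes the window.

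The cost is wording in two documents and one recording instruction. The seriousness part needs no new data and can go into an SAP update or addendum. The downside is that a few events will appear under both treatments in the any-AE rows, which a footnote can explain.
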